5.3.1.2. Coding of Reported Terms

All AE terms will be coded in the database using the Medical Dictionary for Regulatory Activities (MedDRA) coding dictionary.

All tables will show the AE preferred terms grouped into system organ class. Subject listings will also show the reported terms. Any other coding levels will only be shown in a listing summarizing coding unless explicitly mentioned otherwise.

5.3.1.3. Allocation of Adverse Events to Analysis Periods

All AEs will be placed into analysis periods considering their start date, aiming to report the incidence of these events only in the analysis period during which they started.

The general rule for allocation of AEs to analysis periods follows:

$$\text{Analysis period start date} \leq \text{AE start date} \leq \text{analysis period end date}$$

If the start date of an AE is missing or incomplete to a level preventing a clear allocation of the AE to one single analysis period and no flag indicating timing relative to study medication is available, a worst-case consideration (see below) will be done aiming to allocate the AE to one single analysis period, if possible. When a worst-case consideration is needed, the end date of the AE, if and as available, should also be considered; if such AEs clearly end on a given point, this will exclude the possibility to allocate the AE to an analysis period after that point.

- An AE which according to the available information of its start date could belong to the screening as well as to the treatment period will only be placed in the treatment period.

⁶ 'Worsening' is defined as worsening in at least one of the following attributes: seriousness, severity, relationship and/or action taken.

- An AE which according to the available information of its start date could belong to the treatment period as well as to the follow-up period will only be placed in the treatment period.
- An AE with a missing start date will be allocated to the treatment period.

5.3.1.4. Treatment Relatedness

Following the guideline ICH-E3 Structure and Content of Clinical Study Reports (Step 4 Version), the originally reported relatedness to study drug of an AE will be dichotomized as follows:

- *Not study drug related*: all non-missing weaker levels of relatedness than ‘possibly drug related’.
- *Study drug related*: ‘possibly drug related’ and all stronger levels of relatedness (this class also includes any missing drug relatedness, as a worst-case consideration).

Only this dichotomized relatedness will be used in tables and can apply to different study drugs when relatedness has been collected separately per study drug; relatedness as originally reported will only be listed.

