9.2.1. Assessment of Causality

The investigator is responsible for assessing the causal relationship to IMP(s) administration or study procedures (e.g. invasive procedures such as venipuncture) based on her/his clinical judgment. The following decision choice will be used by the investigator to describe the causality assessment between the reported event or laboratory test abnormality and the IMP.

- **Unrelated:**
Time relationship to drug intake is improbable. Related to other etiologies such as concomitant medications or subject's clinical state.
- **Unlikely:**
Time relationship to drug intake is improbable (but not impossible). Concomitant disease or other drugs provide plausible explanations.
- **Possible:**
Time relationship to drug intake is reasonable. Event or laboratory test abnormality, could also be explained by disease or other drugs. Information on IMP withdrawal may be lacking or unclear.
- **Probable:**
Time relationship to drug intake is reasonable. Unlikely to be attributed to concurrent disease or other drugs. Response to withdrawal is clinically reasonable and rechallenge not required.
- **Certain:**
Time relationship to drug intake is plausible. Cannot be explained by concomitant disease or other drugs. Response to withdrawal is plausible (pharmacologically, pathologically). Event definitive pharmacologically or phenomenologically (i.e. an objective and specific medical disorder or a recognized pharmacological phenomenon). Rechallenge satisfactory, if ethical and necessary.

It should be emphasized that ineffective treatment (worsening of the disease by the IMP) should not be considered as causally related in the context of AE reporting.

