5.3.1.7. Presentation of Results

The analysis will focus on AEs reported during the treatment period. AEs reported during the screening or follow-up period will only be listed.

All adverse events tables will show the number of subjects with TEAEs.

A summary table will be provided, showing the number (percent) of subjects with at least one:

- TEAE
- serious TEAE
- TEAE leading to death
- TEAEs by worst severity
- TEAE that was considered related to GLPG1205/placebo
- TEAE that was considered related to pirfenidone
- TEAE that was considered related to nintedanib
- TEAE for which GLPG1205/placebo was reduced
- TEAE for which GLPG1205/placebo was temporarily stopped
- TEAE for which GLPG1205/placebo was permanently stopped
- TEAE for which pirfenidone was reduced
- TEAE for which pirfenidone was temporarily stopped
- TEAE for which pirfenidone was permanently stopped
- TEAE for which nintedanib was reduced
- TEAE for which nintedanib was temporarily stopped
- TEAE for which nintedanib was permanently stopped

For each line, the difference in percentage of subject with an AE between placebo and GLPG1205 will be included, together with the 95% CI of the difference using the method of Miettinen and Nurminen.

Frequency tabulations, by system organ class and preferred term, of the number (percent) of subjects with a TEAE will be presented. Similar tables will be provided (by worst severity) for TEAEs of grade 3/4, TEAEs related to GLPG1205/placebo and for TEAEs related to SOC.

Serious adverse events (including AEs leading to hospitalization), AEs leading to death, leading to respiratory-related hospitalization (as reported by the investigator), of grade 3/4, leading to discontinuation of GLPG1205/placebo, leading to a temporary stop or dose reduction of GLPG1205/placebo, leading to a permanent stop, temporary stop, or dose reduction of SOC, pre- and post-treatment adverse events will be listed.

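### The missing-equals-related rule in SAP 5.3.1.4 has no exposure condition, so a blank answer for pirfenidone or nintedanib in a subject who never took it would count as a related TEAE

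*SAP*

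**What the plan says.** SAP 5.3.1.4 reduces the investigator's causality grade to two classes. The not-related class takes "all non-missing weaker levels of relatedness than ‘possibly drug related", so a blank cannot fall there. The related class takes possible and stronger grades, and "this class also includes any missing drug relatedness, as a worst-case consideration". On scope, the section states: "Only this dichotomized relatedness will be used in tables and can apply to different study drugs when relatedness has been collected separately per study drug".

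SAP 5.3.1.7 then lists, as separate rows of the AE summary table, "TEAE that was considered related to pirfenidone" and "TEAE that was considered related to nintedanib", beside the row for GLPG1205/placebo. It adds a frequency table by system organ class and preferred term for TEAEs related to standard of care. For the summary table, "For each line, the difference in percentage of subject with an AE between placebo and GLPG1205 will be included", with a 95% Miettinen-Nurminen interval. SAP 4.2 makes the standard-of-care-related table an interim output as well.

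Under SAP 3.5.3 the denominator for event data is every subject in the analysis set and period. Under SAP 5.3 that set is the FAS.

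In the protocol, Section 9.2.1 says: "The investigator is responsible for assessing the causal relationship to IMP(s) administration or study procedures". Its five-grade scale is worded for the IMP and has no 'not applicable' grade. Section 7.3.5.2 nevertheless plans TEAE summaries by relationship to IMP or standard of care.

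**The concern.** A worst-case rule for missing causality is sensible when the subject was exposed and the investigator left the question unanswered. It makes no sense when the subject never took the drug, because the attribution is then impossible.

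Non-takers are part of the design. Background therapy is nintedanib, pirfenidone or neither, and Protocol 7.1 works with an aim of half the population on an antifibrotic and half on neither. For each drug taken singly, non-takers are therefore likely to be the majority of the FAS.

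At stake is whether the relatedness rows for pirfenidone, nintedanib and standard of care can be read at all. If most of a row consists of unexposed subjects with some TEAE, its percentage is not a rate of antifibrotic-related events, and its arm difference largely compares any-TEAE rates among non-takers.

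**Working it through.** The documents give no figure for this point, so there is none to reproduce. The check has two parts.

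**1. What the rule does to a blank**

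- Not related requires a non-missing answer, and missing goes to related. A blank is therefore related.
- Only the two-class version enters tables, and SAP 5.3.1.4 is the only place where it is defined.
- The tables count all FAS subjects (SAP 3.5.3, 5.3). No section limits the pirfenidone, nintedanib or standard-of-care rows to takers, defines a 'not applicable' answer, or exempts non-takers.
- Does the rule reach these drugs? The wording is that it "can apply to different study drugs when relatedness has been collected separately per study drug". Elsewhere in the SAP, study drug means GLPG1205/placebo, so this is an inference. But the trial has only one study drug in that narrow sense, and if 5.3.1.4 does not govern the pirfenidone and nintedanib rows, the SAP has no rule for them.

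**2. Size if every non-taker's field is blank (illustration)**

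From the documents: about 60 subjects randomised 2:1, so 40 and 20. Assumed: the split between background groups; q, the share of subjects with at least one TEAE; and r, the share of takers with a truly related TEAE.

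*Equal strata, GLPG1205 arm, one drug:*
- Non-takers: 40 × 2/3 = 26.7
- Wrongly counted at q = 0.80: 26.7 × 0.80 = 21.3, and 21.3/40 = 53%
- Upper limit, q = 1: 26.7/40 = 67%
- Lower limit, no blanks: 0%

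*Whole trial, N = 60:* subjects counted = takers × r + non-takers × q, with r from 0.10 to 0.30 and q from 0.60 to 0.90.

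| Split (nintedanib/pirfenidone/neither) | Truly related to pirfenidone | Blank non-takers | Counted under literal rule |
|---|---|---|---|
| 20/20/20 | 20 × r = 2 to 6 | 40 × q = 24 to 36 | 26 to 42 (43% to 70%) |
| 15/15/30 | 15 × r = 1.5 to 4.5 | 45 × q = 27 to 40.5 | 28.5 to 45 (47.5% to 75%) |

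The second row follows the 50:50 aim of Protocol 7.1, with an assumed even split between the two drugs. The 67% ceiling belongs to equal strata; with 45 of 60 non-takers it would be 75%.

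*Arm difference.* The artefact is w × (q in GLPG1205 − q in placebo), where w is the non-taker share.
- Equal q: 0
- q of 0.85 against 0.70: 2/3 × 15 = 10 points, or 0.75 × 15 = 11.3 points

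Even with equal q, precision is lost. Take 20/20/20 with q = 0.75 and r = 0.10: the row moves from 2/60 = 3.3% to 32/60 = 53.3%. A simple Wald half-width, 1.96 × √[p(1−p)(1/40 + 1/20)], moves from 9.6 to 26.8 points. This approximates the planned interval, but it shows the few true events being swamped.

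**The case against.** The strongest objection is that the error needs something the documents do not show. The field must be blank for non-takers, and the program must read that blank as missing. SAP Section 1 places technical derivation details in a separate document, and a question that does not apply need not be treated as missing data. This stands, and it is why the range starts at zero.

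The wording in 5.3.1.4 is permissive, saying the rule can apply to different study drugs. That also stands, though the alternative leaves these rows with no rule.

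A reader might infer from Protocol 9.2.1 that causality to the antifibrotics is never collected, so the fields must be blank. That does not follow: Protocol 7.3.5.2 plans summaries by relationship to standard of care.

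A reader might also infer that the rule would hide a real increase in antifibrotic toxicity from adding GLPG1205. The documents do not support that. SAP 5.3.1.8 tabulates events of specific interest for each antifibrotic by arm and by stratum and arm, and SAP 5.3.1.7 has rows for pirfenidone and nintedanib being reduced, interrupted or stopped. None of these uses relatedness.

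Finally, the artefact would be noticed. SAP 5.3.1.10 repeats the AE summary by stratum, where pirfenidone-related events would appear in the neither group, and relatedness as originally reported is listed. This would expose the problem but not correct the tables. Stratified randomisation should also keep non-taker shares similar across arms, which limits the false difference but not the inflation or the loss of precision.

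**Conclusion.** The gap is in the text: SAP 5.3.1.4 makes any missing relatedness related, without asking whether the subject took the drug, for rows whose denominator is the whole FAS. Whether it causes error depends on the CRF and the derivations document, neither of which is available. If non-takers' fields are blank, the pirfenidone, nintedanib and standard-of-care relatedness rows are inflated, and their arm differences and intervals say little.

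The size of about 53% of the GLPG1205 arm per drug rests on three assumptions: equal strata, an 80% TEAE rate, and blanks for every non-taker. The range under equal strata is 0 to 67%. It is not a forecast.

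The effect is confined to those rows. Relatedness to GLPG1205/placebo, the events-of-specific-interest tables, the standard-of-care reduction and stop rows, and all efficacy analyses are untouched. Safety is descriptive, without formal testing. The point is worth correcting because the rule is explicit and the correction is cheap.

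**What to change.** Amend SAP 5.3.1.4 so that missing counts as related only for a drug the subject had taken on or before the AE start date. Otherwise set relatedness to that drug to 'not applicable' and leave it out of the related counts. For the pirfenidone, nintedanib and standard-of-care relatedness rows, use subjects exposed to the drug concerned as the denominator.

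Base exposure on actual intake records rather than baseline stratum, since subjects may start or switch these drugs after randomisation. Two details should be settled in the same text:
- whether intake that ended before the first IMP dose counts as exposure, because SAP 5.1.1 recognises subjects who had already stopped one or both drugs;
- that dates too incomplete to order are treated as exposed, which keeps the worst-case intent.

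The cost is a sentence or two in the SAP, one programming condition and a changed denominator for these rows. The intake data are already collected (Protocol 4.3.4.2) and already used in SAP 5.1.6.4. If the CRF already codes 'not applicable', the related counts do not change and the text simply documents the handling. This changes the analysis only and has no bearing on clinical management.

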5.3.1.5. Worst-Case Selections

When cross-tabulating AE preferred terms versus an AE attribute (e.g. severity), only the worst-case within each analysis period will be considered, i.e. when a subject has more than once the same AE preferred term reported in the same analysis period, the subject will be counted only once and will be shown under the worst outcome (e.g. the worst severity for that AE in the concerned analysis period). If this happens in 2 different analysis periods, the AE is reported twice: once in each analysis period.

5.3.1.6. Calculation of Relative Days and Duration

For each newly reported event, and reported worsening or improvement of an existing event, the start day in the study (the day of the AE start date relative to the date of first study drug administration), the start day in the analysis period, and the duration (in days) will be calculated. In addition, the relative day and duration will be derived for the entire event; that is, the full evolution of the event, including the initial reporting and all subsequent worsening and/or improvement.

Relative days and durations will only be listed.

See Section [3.3.1](#) for the calculation of relative days.

5.3.1.7. Presentation of Results

The analysis will focus on AEs reported during the treatment period. AEs reported during the screening or follow-up period will only be listed.

All adverse events tables will show the number of subjects with TEAEs.

A summary table will be provided, showing the number (percent) of subjects with at least one:

- TEAE
- serious TEAE
- TEAE leading to death
- TEAEs by worst severity
- TEAE that was considered related to GLPG1205/placebo
- TEAE that was considered related to pirfenidone
- TEAE that was considered related to nintedanib
- TEAE for which GLPG1205/placebo was reduced
- TEAE for which GLPG1205/placebo was temporarily stopped
- TEAE for which GLPG1205/placebo was permanently stopped
- TEAE for which pirfenidone was reduced
- TEAE for which pirfenidone was temporarily stopped
- TEAE for which pirfenidone was permanently stopped
- TEAE for which nintedanib was reduced
- TEAE for which nintedanib was temporarily stopped
- TEAE for which nintedanib was permanently stopped

For each line, the difference in percentage of subject with an AE between placebo and GLPG1205 will be included, together with the 95% CI of the difference using the method of Miettinen and Nurminen.

Frequency tabulations, by system organ class and preferred term, of the number (percent) of subjects with a TEAE will be presented. Similar tables will be provided (by worst severity) for TEAEs of grade 3/4, TEAEs related to GLPG1205/placebo and for TEAEs related to SOC.

Serious adverse events (including AEs leading to hospitalization), AEs leading to death, leading to respiratory-related hospitalization (as reported by the investigator), of grade 3/4, leading to discontinuation of GLPG1205/placebo, leading to a temporary stop or dose reduction of GLPG1205/placebo, leading to a permanent stop, temporary stop, or dose reduction of SOC, pre- and post-treatment adverse events will be listed.

5.3.1.8. Adverse Events Related to Nintedanib or Pirfenidone

To investigate the events expected to be associated with pirfenidone and/or nintedanib a frequency table by system organ class and preferred term, by treatment group, as well as by stratum and treatment group, will be provided for the preferred terms of events of specific interest to nintedanib (e.g. diarrhea, nausea, vomiting, dehydration, weight decrease and decreased appetite adverse events) and pirfenidone (e.g. photosensitivity reactions, nausea, diarrhea, dyspepsia, vomiting, gastro-esophageal reflux disease, and abdominal pain). The full list of preferred terms to be investigated will be detailed before unblinding for the final CSR.

5.3.1.9. EudraCT Adverse Events Reporting

For the purpose of EudraCT reporting, the following tabulations will be created:

Frequency tabulations, by system organ class and preferred term, of the number (percent) of subjects with serious TEAE and the number of serious TEAEs will be presented. A similar table will be provided for all non-serious TEAEs.

5.3.1.10. Subgroup Analyses

The AE summary table, the frequency table by system organ class and preferred term, and the frequency table for events of specific interest will be provided for each stratum (3 strata; nintedanib, pirfenidone, neither).

5.3.2. Laboratory Safety

5.3.2.1. Available Data

Laboratory tests scheduled are described in the protocol. In addition, the derived laboratory tests described in Section 5.3.2.2 will be added.

The statistical analyses will only present results in Standard International (SI) units. Other units will not be presented.

Only data provided by the central laboratory will be used.

5.3.2.2. Derivation Rules

Derived Laboratory Tests

Creatinine clearance (C_{Cr}), estimated according to Cockcroft-Gault calculation:

$$C_{Cr} \text{ (in mL/min)} = [(140 - \text{age}) \times \text{weight}] / [72 \times S_{Cr}] \text{ (x 0.85 for women), with } S_{Cr} = \text{serum creatinine in mg/dL, age in years, and weight in kg}$$

For the calculation of estimated creatinine clearance, the age at screening and the weight, closest to the assessment for which creatinine clearance is calculated, will be used.

Fasted and Non-Fasted Results

Laboratory tests that are sensitive to the fasting status: glucose, triglycerides.

For these laboratory tests, descriptive statistics and tabulations of Common Terminology Criteria for Adverse Events (CTCAE) toxicities (fasting only) will be shown by fasting status. Tabulations of scorings according to normal ranges will be created for both fasting and non-fasting results pooled. Laboratory results for which the fasting status is missing, will be considered as taken fasted.

5.3.2.3. Definition of Toxicity Grades

Toxicity grades will only be derived for laboratory tests specified in this section. For other tests, only the classification according to normal ranges will be used (Section 5.3.2.4).

Toxicity grades will be determined as implemented in the attached table (appendix) based on CTCAE, v5.0: November 27, 2017.

Note: when no explicit grade (e.g. “G1”) is included, the categories will be labeled as indicated by the thresholds.

In addition, the following criteria will be used:

Table 5 Additional Toxicity Grading

Tests	Thresholds (Conventional Units)	Thresholds (SI Units)
Hematology		
Eosinophiles relative count	>5%	>5%
Coagulation		
Prothrombin time (PT)	>ULN - 1.5 x ULN >1.5 - 2.5 x ULN >2.5 x ULN	>ULN - 1.5 x ULN >1.5 - 2.5 x ULN >2.5 x ULN
Chemistry		
Random glucose increased (fasting)	>130 mg/dl	> 7.2 mmol/L
High density lipoprotein (HDL)	<60 mg/dL	<1.554 mmol/L
Low density lipoprotein (LDL)	>160 mg/dL	>4.144 mmol/L

To investigate elevated liver function, the following additional grading (based on the exclusion and discontinuation criteria in the CSP) is defined.

Table 6 Additional Toxicity Grading for Liver Function

Tests	Thresholds
AST	AST >1.5 - <=3 x ULN AST >3 - <=5 x ULN AST >5 - <=8 x ULN AST >8 x ULN
ALT	ALT >1.5- <=3 x ULN ALT >3 - <=5 x ULN ALT >5 - <=8 x ULN ALT >8 x ULN

Tests	Thresholds
AST / ALT combination	ALT and/or AST >1.5 - <=3 x ULN AST and /or ALT >3 - <=5 x ULN AST and /or ALT >5 - <=8 x ULN AST and /or ALT >8 x ULN
AST / ALT / total bilirubin combination	Bilirubin >2 x ULN AND AST or ALT >3 x ULN
AST / ALT / INR combination	INR >1.5 AND AST or ALT >3 x ULN
AST / ALT / eosinophiles relative count combination	Eosinophils >5% AND AST or ALT >3 x ULN

5.3.2.4. Definition of Non-Graded Abnormalities

For laboratory tests provided by the laboratory, the position of the actual analysis values versus their normal ranges will be determined directly by using the position indicator provided in the database as reported by the central laboratory, expressing the classes for these analysis values as low (L), normal (N) or high (H). L, N, and H are further referred to as non-graded abnormalities.

Only for tests for which no toxicity gradings are specified in Section 5.3.2.3, analysis of the classification according to normal ranges will be done.

